3 SUBJECT SELECTION AND WITHDRAWAL

A total of 20 participants will be recruited for this study and all data will be collected at UNC-CH. No specific plans have been made to enroll participants from vulnerable populations.

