5.1 SCREENING

The screening process will involve a telephone call with the potential participant to inform of expectations and determine eligibility. A researcher will conduct a screening with each participant prior to scheduling the first session. If a participant is determined to be ineligible, data from the screening will be retained.

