5.2 STIMULATION SESSIONS

Participants will undergo two sessions with the same procedure; the only change will be the stimulation condition.

5.4.1 SESSION 1

In the initial session, participants will be explained the procedure and reminded of their expectations and rights (informed consent). After obtaining consent, a urine drug test and pregnancy screening will be administered. Once they are both determined to be negative, the stimulation, EEG, and heart rate electrodes will be applied. Participants will then undergo a ten-minute resting state block to record EEG activity. Participants then provide a baseline saliva sample and receive 40 minutes of either 10Hz tACS or sham stimulation (depending on the randomized condition) while watching the 'Reefscape' video. After the stimulation, the participant will complete the stimulation adverse effects questionnaire, and will then provide a final saliva sample. The study coordinator will remove all equipment, and the participant will fill out the final two questionnaires and receive \$20 in compensation.

5.4.2 SESSION 2

The procedure for the second session will follow the same timeline as the first, with the exclusion of informed consent, urine drug test, and pregnancy screening processes. Participants will receive \$40 in compensation at the end of this session.

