10.2 METHODS AND TIMING FOR ASSESSING, RECORDING, AND ANALYZING SAFETY PARAMETERS

10.2.1 ADVERSE EVENTS

All AEs, including local and systemic reactions not meeting the criteria for “serious adverse events”, will be captured on the appropriate CRF. In addition, the AE Report Form will be completed by the study coordinator (Appendix B). The AE Report Form includes the following:

- What is known about the therapy
- What is known about previous reported side effects
- If the AE occurred in temporal relation to the therapy
- Whether or not the AE improves or disappears when treatment is stopped
- Whether the AE is worsening of baseline symptoms
- Whether the AE is related to concurrent medical condition or medication use

Once complete, this form will be given to the PI and Co-I, who will review, comment, and sign this form. Completed forms will be placed in the participant’s folder.

In addition, the study coordinator will document any AE occurrence on the AE log (*Appendix D*), which includes information such as the date of the AE, severity, relationship to the treatment (assessed by the PI and Co-I*), actions taken, and outcome(s). The log will be reviewed and initialed by the PI 72 hours after being completed. All AEs occurring during the clinical trial will be documented appropriately regardless of relationship to tACS. All AEs will be followed to adequate resolution and will be graded for severity and relationship to study treatment. Any medical condition noted at the initial session will be considered at baseline and not reported as an AE.

All AEs will be graded for severity using the following guidelines:

- **ASYMPTOMATIC.** The participant is exhibiting no symptoms due to this event; no treatment needed.
- **MILD.** Event results in mild or transient discomfort, not requiring intervention or treatment; does not limit or interfere with daily activities (e.g., insomnia, mild headache)
- **MODERATE.** Event is sufficiently discomforting so as to limit or interfere with daily activities; may require interventional treatment (e.g., fever requiring antipyretic medication). In the case of a moderate AE, the medical advisor may recommend an over the counter medication.
- **SEVERE AND UNDESIRABLE.** Event results in significant symptoms that prevent normal daily activities; may require hospitalization or invasive intervention (e.g., anemia resulting in blood transfusion).

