APPENDIX A: SCHEDULE OF EVENTS

	Phone Screening	Day 1 of Stimulation	Day 2 of Stimulation
Procedures			
Provide Verbal Consent	x		
Signed Consent Form		x	
Assessment of Eligibility Criteria	x	x	
Urine Pregnancy Test		x	
Urine Drug Test		x	
Baseline Assessments (PSS, CD-RISQ, PSQI)		x	
Saliva Sample		x	x
Stimulation		x	x
Stimulation Questionnaire		x	x
Saliva Sample		x	x
Final Questionnaires (PANAS, STAI)		x	x

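### The AE baseline rule is tied to the initial session, which includes the first stimulation, so conditions that begin during Session 1 could lose AE status

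*Combined protocol and SAP*

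**What the plan says.** The rule is in section 10.2.1 (Adverse Events): "Any medical condition noted at the initial session will be considered at baseline and not reported as an AE". Two sentences before it, the same paragraph commits to documenting every AE that occurs in the trial, whether or not it is related to tACS.

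Section 5.2 describes the initial session under the subheading Session 1. After consent, urine tests, electrode placement and a resting EEG block, "Participants then provide a baseline saliva sample and receive 40 minutes of either 10Hz tACS or sham stimulation". Then: "After the stimulation, the participant will complete the stimulation adverse effects questionnaire, and will then provide a final saliva sample". Appendix A agrees. Its column headed "Day 1 of Stimulation" contains the consent form, the eligibility check, the baseline scales, the stimulation and the stimulation questionnaire.

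There is no separate on-site baseline visit. Section 5.1 says: "The screening process will involve a telephone call with the potential participant to inform of expectations and determine eligibility".

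**The concern.** A baseline rule is meant to separate what a participant brought to the trial from what arose after exposure. This one draws the line at a visit, and that visit includes the first exposure. It sets no condition that onset precede stimulation.

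What is at stake is formal AE status. Under section 10.2.1, that status leads to the AE report form, review by the PI and Co-I, the AE log, grading for severity and relationship, and follow-up to resolution. Section 9.4 also names a rise in event frequency among the findings that might prompt a safety review, and such a rise is harder to see if first-exposure effects are filed as baseline.

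There is a second effect. The AE form (section 10.2.1 and Appendix B, item 4) asks whether the event is a worsening of baseline symptoms. If a Session 1 stimulation effect has been labelled baseline, the same symptom at Session 2 would be judged against the wrong reference.

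**Working it through.** **Inputs**
- Participants: 20 (section 3: "A total of 20 participants will be recruited for this study and all data will be collected at UNC-CH").
- Visits per participant: 2, each with one stimulation (section 4; Appendix A).
- Stimulation codes: 40 (section 4.1.1).
- Order of conditions: randomized for each participant (section 6.2), with no statement that the order is balanced.

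**Step 1: reproduce the plan's own count.** 20 × 2 = 40 stimulation sessions, which matches the 40 codes.

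**Step 2: sessions that fall under the rule.** Each participant has one initial session, so 20 × 1 = 20. The share is 20 / 40 = 50%. If the rule covered only conditions present before the first stimulation starts, it would reach 0 of 40.

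**Step 3: split by condition.** If 10 participants receive active stimulation first (an assumption), 10 of the 20 active sessions and 10 of the 20 sham sessions are initial sessions, or 50% of each. Under simple randomization with probability 0.5 (also an assumption), a plausible range is 6 to 14 active-first. That gives 6/20 = 30% to 14/20 = 70% of active sessions, with the complement for sham. The rule could therefore fall unevenly on the two conditions by chance.

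**Step 4: apply the two sentences to one case.** Take a headache, which is listed on the questionnaire (section 10.1), that starts midway through the Session 1 stimulation and is reported on the questionnaire afterwards.
- Under the commitment to document all AEs, it gets an AE form, a log entry and a grade.
- Under the baseline rule read literally, it was noted in the initial session, so it is baseline and is not reported as an AE.

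If the headache counts as a medical condition, staff cannot follow both sentences.

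**Step 5: what else in Session 1 could bring a condition to notice.** Medical history is taken at the telephone screen (section 6.1). Before stimulation on Day 1, Appendix A lists an eligibility check, urine tests and the PSS, CD-RISC and PSQI scales. The only scheduled list of symptoms at that visit is the questionnaire given after stimulation. The eligibility check could reveal a pre-existing condition, but the rule does not confine itself to that step.

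**The case against.** The strongest reply is that the sentence concerns a medical condition, and that the protocol uses this term for background illness. The AE form asks separately whether an AE is related to a concurrent medical condition, while stimulation effects are called side effects or reactions. On that reading the rule excludes only pre-existing illness, and the two sentences do not conflict. This is probably the intent. It lowers the chance of misuse but does not remove it, because nothing in the sentence limits onset to the time before stimulation.

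The second reply is that Session 1 safety information is collected anyway. This stands. The questionnaire is given after both sessions (sections 6.3 and 10.1), and staff check in during stimulation. Moderate or severe effects are discussed and noted, with the PI contacted according to intensity (section 8.3). SAEs have their own recording and IRB reporting text. What is exposed is AE status, not every record of the symptom.

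A reader might go further and infer that half of all AEs would be lost, or that the tACS-versus-sham safety comparison would rest on Session 2 alone. The documents support neither. The 50% counts sessions, and an effect first noted after the participant leaves Session 1 remains reportable. Section 11 plans no AE comparison between conditions: its primary outcomes are biomarkers and its secondary outcomes are EEG changes. Any descriptive comparison of side effects could use the questionnaire ratings from both sessions.

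**Conclusion.** The point holds as a fault in a stated rule: followed to the letter, it can reclassify an effect of the first stimulation as baseline, contrary to the commitment to document all AEs in the same paragraph. It reaches 20 of 40 stimulation sessions (50%). The number of AEs affected cannot be derived from the documents, since it depends on how often conditions arise within Session 1 and on how staff read the sentence. Misclassification is a risk created by the wording, not a certainty.

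The 50% rests only on 20 participants completing two sessions each. The split between active and sham also rests on the assumed form of randomization. The planned biomarker and EEG analyses are not affected. The correction is still worth making, because the rule governs AE capture at first exposure to the study stimulation and costs almost nothing to repair.

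**What to change.** Reconcile the two sentences in section 10.2.1 by replacing the baseline sentence with wording such as: *A medical condition present before stimulation starts at Session 1 is baseline. Any condition that begins or worsens after that point, including later in Session 1, is recorded as an AE.* The AE form's question about worsening of baseline symptoms should use the same definition.

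This needs no new visit, assay or questionnaire. It does require staff to note onset relative to the start of stimulation, which the AE form already approaches through its question on temporal relationship. The downside is a slightly higher AE count and a few more AE forms to complete and review.

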10.2.1 SERIOUS ADVERSE EVENTS

Serious Adverse Event (SAE): An SAE, as defined by the NIH, consists of adverse events that result in death, require either inpatient hospitalization or the prolongation of hospitalization, are life-threatening, result in a persistent or significant disability/incapacity or result in congenital anomaly/birth defect. Other important medical events, based upon appropriate medical judgment, may also be considered Serious Adverse Events if a trial participant's health is at risk and intervention is required to prevent an outcome mentioned.

All SAEs will be recorded on the Serious Adverse Events Form (Appendix B), documented in the UE/SAE log and reported to the IRB. The SAE Form will be completed by the study coordinator, and includes information relating to the onset and nature of the SAE, relationship to the study treatment, seriousness of the SAE, treatment required as a response to the SAE, and outcome. This form will be filed in the participant's folder at the resolution of the event. The study coordinator will complete the UE/SAE log (Appendix D) which includes information such as the date of the event, time at which the study team was informed of the event, details, when the IRB was notified, and the date that the SAE form was completed.

10.2.2 UNANTICIPATED PROBLEMS

Unexpected Events (UE) will be recorded on the UE/SAE log (Appendix D) and will include information such as the date of the event, when the study team was informed of this event, details of the event, when the IRB was notified, and whether the SAE form was completed. The IRB will be notified of each UE that may occur during the study.

The Office for Human Research Protections (OHRP) considers unanticipated problems involving risks to subjects or others to include, in general, any incident, experience, or outcome that meets all of the following criteria:

- unexpected (in terms of nature, severity, or frequency) given (a) the research procedures that are described in the protocol-related documents, such as the IRB-approved research protocol and informed consent document; and (b) the characteristics of the subject population being studied;
- related or possibly related to participation in the research (in the guidance document, possibly related means there is a reasonable possibility that the incident, experience, or outcome may have been caused by the procedures involved in the research); and
- suggests that the research places subjects or others at a greater risk of harm (including physical, psychological, economic, or social harm) than was previously known or recognized.

If an UE occurs the IRB will be notified and the study will be adjusted as needed to protect the health and safety of the participants. Depending on the nature of the UE, the research protocol, inclusion/exclusion criteria, and informed consent will be changed to reflect the possibility of this event reoccurring. During this time, no new participants will be recruited and the research procedures for currently enrolled participants will be stopped. Each UE will be recorded and reported throughout the study.

10.3 REPORTING PROCEDURES

We will be adopting the following table for reporting procedures:

What Event is Reported	When is Event Reported	By Whom the Event is Reported	To Whom the Event is Reported
Fatal or life-threatening unexpected, suspected serious adverse reactions	Within 24 hours of initial receipt of information	Investigator	Local/internal IRBs
Non-fatal, non-life threatening unexpected, suspected serious adverse reactions	Within 48 hours of initial receipt of information	Study Coordinator	Local/internal IRBs/Institutional Officials, DSMB
Unanticipated adverse device effects	Within 10 working days of investigator first learning of effect	Investigator	Local/internal IRBs
Unanticipated problem that is not an SAE	Within 7 days of the investigator becoming aware of the problem	Investigator	Local/internal IRBs/Institutional officials
All Unanticipated Problems	Within 30 days of the IRB's receipt of the report of the UP from the investigator	IRB	OHRP
		Investigator	External IRBs

10.3.1 REPORTING OF PREGNANCY

Pregnancy tests will be administered on Day 1 of Stimulation to all women of child-bearing potential. There are no studies that suggest tACS would interfere with pregnancy. However, should a participant become pregnant during the study, their participation will be immediately terminated.

10.4 TYPES AND DURATION OF FOLLOW-UP OF PARTICIPANTS AFTER ADVERSE EVENTS

The study coordinator will follow up within one week of an adverse event.

11 STATISTICAL PLAN

The statistician for this study is [name].

11.1 STATISTICAL ANALYSIS STRATEGIES

11.1.1 MEASURES OF INTEREST

The primary outcomes of this study will be the quantified changes in cytokine, alpha-amylase, and cortisol activity.

EEG changes will be quantified and analyzed as secondary outcomes.

11.1.2 AIMS

Aim 1: Characterize and compare the sham and tACS stimulation conditions in terms of the measures of interest, stated above. These outcomes will be used to decide whether the tACS regimen should be evaluated in a larger controlled trial.

Aim 2: Obtain statistical estimates needed to plan a future, large-scale clinical trial.

11.1.2 ANALYSIS

Statistical analyses will be performed to test the null hypothesis indicated in section 2.4 *Study Aims/Hypothesis*. Data from the saliva samples will be compared within and between the two treatment sessions for each participant. Within sessions, the post-treatment sample will be compared to both the post-stress and the baseline, to determine the changes in biomarker levels as a result of the stimulation. Then, these two differences will be compared to the same differences from the corresponding treatment session for the participant, in order to determine if the tACS treatment had a significant effect on NK cell count. Biomarkers will also be correlated with each other to confirm the previously established relationship between sympathetic activation and immune response.

A significant difference (p -value less than or equal to 0.05) between the treatment conditions in within-session activity of any of the biomarkers will constitute a rejection of the null hypothesis. Any outcome with a p value > 0.05 will be regarded as inconclusive. Confidence intervals of 95% will be reported for all statistical estimates. Additionally, interpretation of outcomes will focus on estimated changes in levels of biomarkers, rather than just significance. Data will be represented in a mixed linear model to account for correlated data and unequal variances. In the event that the primary outcomes do not produce significant results, exploratory analyses will be conducted on the existing data to determine new hypotheses.

Any incomplete or missing data will be excluded from analysis; if time permits, further data collection will be conducted to account for the loss.

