6.4.2 SALIVA SAMPLES

We will be collecting a saliva sample at the first session. This sample will be used to test for a single nucleotide polymorphism in the BDNF gene whose presence may have an influence on effectiveness of brain stimulation. Within the central nervous system, BDNF regulates survival, proliferation, and synaptic growth as well as directly influences synaptic plasticity in the adult human brain (Antal et al., 2010). Egan et al. (2003) demonstrated that Val66Met, a single nucleotide in the BDNF gene, has function consequences in healthy humans, including decreased episodic memory and hippocampal inducing a reduction in recall capacity. This polymorphism is common in over one third of the Caucasian population (65% Val66Val to 35% Val66MET) (Pezawas et al, 2004; Hariri and Weinberger, 2003). Kleim et al. (2006) found that individuals with the Val/Val polymorphism respond to tDCS and transcranial magnetic stimulation (TMS) treatments with expected change, whereas, individuals expressing Val/MET allele do not. These authors indicate the difference to be caused by the impairment in synaptic plasticity caused by the Val/MET allele. These findings suggest that individual efficacy of treatments using brain stimulation may be partially genetically predetermined and should be taken into account when performing such procedures. Accordingly, we will conduct genotyping of all participants in this study in order to assess BDNF status. We will perform exploratory analyses in which we group participants by BDNF status.

We will also be collecting two saliva samples at each session to test for a cytokine panel, salivary alpha-amylase, and cortisol as measures of immunity and stress.

INSTRUCTIONS FOR SPECIMEN PREPARATION, HANDLING, AND STORAGE. The saliva samples for BDNF testing will be collected using 2mL DNA collection kit from DNA Genotek. Before sample collection, it is imperative that the participant does not eat, drink, smoke or chew gum for at least 30 minutes before providing a sample. Once the participant provides the 2mL sample, the collection tube is closed and a liquid from the lid will be released into the tube. The original lid will be removed and replaced with a small cap and the tube will be agitated for 5 seconds. The sample is then returned to the plastic packaging and labeled with the date of collection, the study name, and the participant ID. These samples are kept in a secure location until the completion of data collection.

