7.3 PREPARATION AND ADMINISTRATION OF STUDY INVESTIGATIONAL PRODUCT

After participants have completed the questionnaires, they will be comfortably seated. The research team will first measure their heads electrode placement using the 10-20 system. Participants will then be fitted with the 3 electrodes for stimulation. The participant will be in the relaxed yet, experimentally controlled state by watching a nature movie. One session of stimulation will be performed per visit for 40 minutes. During the 10 Hz tACS

condition, participants will have a 10 second ramp in and ramp out with 40 minutes of stimulation for a total of 2420 seconds. Stimulation waveforms are sine-waves with a peak-to-peak amplitude of 2 mA. The sham stimulation will include 10 seconds of ramp in to 1 minute of 10 Hz tACS with a ramp out of 10 seconds for a total of 100 seconds of stimulation. Electrodes will be saline soaked, 5x5cm and placed over F3 and F4 with a 5x7cm placed over CZ as a return electrode.

Stimulation devices will be preprogrammed and codes will be randomized to one of the two experimental arms. Researchers will enter the participant-specific code into the App that controls the stimulation and monitor participants during the 40 minutes of the stimulation.

The study coordinator and/or the research assistant will be thoroughly trained and have trainings documented on the transcranial stimulation device and will be present during all stimulation sessions. *Please see Appendix F for an example of the training documentation log.* To monitor side effects of stimulation a questionnaire will be administered after each stimulation session. *Please see Attachment 1 for an example of the stimulation questionnaire.*

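### Section 11.1.2 needs three biomarker saliva samples per session but the procedures schedule two, so at most one of its two tACS-versus-sham contrasts per biomarker can be computed; the visible text does not place the stress task, leaving the meaning of the remaining contrast unsettled

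*Combined protocol and SAP*

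**What the plan says.** **The analysis.** Section 11.1.2 (Analysis) sets out the comparison for the primary outcomes in two steps. First: "Within sessions, the post-treatment sample will be compared to both the post-stress and the baseline". Second: "Then, these two differences will be compared to the same differences from the corresponding treatment session for the participant". Section 11.1.1 names the primary outcomes as changes in cytokines, alpha-amylase and cortisol.

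**The sampling.** Section 6.4.2 states: "We will also be collecting two saliva samples at each session to test for a cytokine panel, salivary alpha-amylase, and cortisol". The session 1 steps (5.4.1, under section 5.2) place these samples. Before stimulation: "Participants then provide a baseline saliva sample and receive 40 minutes of either 10Hz tACS or sham stimulation". After it: "After the stimulation, the participant will complete the stimulation adverse effects questionnaire, and will then provide a final saliva sample". For session 2: "The procedure for the second session will follow the same timeline as the first". Appendix A has two saliva rows, one on each side of the stimulation row, both marked on both days. Section 6.4.2 also describes one further saliva sample at session 1, taken with a separate DNA kit for BDNF genotyping.

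**The stress task.** The title asks about the immune response to a psychological stressor. Section 8.2.1 says that participants will do a timed mental arithmetic task intended to induce stress, and section 6.1 uses the state STAI to measure anxiety arising from the stress condition. The task does not appear in the session steps (5.4.1, 5.4.2), in the device administration text (7.3) or in Appendix A.

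**The concern.** The analysis refers to a post-stress sample that no procedural section collects. Staff who follow the session steps exactly will produce data on which part of the stated primary analysis cannot be run, and saliva not taken at a time point cannot be recovered later.

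The second problem concerns interpretation. Two samples still give one change per session, but what that change measures depends on where the stress task falls. It could be a net change over stress and recovery, a change that includes reactivity after stimulation, recovery alone, or a change with no response to the task. These are different estimands. Section 11.1.2 (Aims) uses these outcomes to decide whether to run a larger trial and to obtain the estimates for planning it, and an estimate of unsettled meaning serves neither purpose well.

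**Working it through.** **1. Reproduce the plan's own count.** Appendix A: 2 saliva rows × 2 days = 4 biomarker samples per participant, and 4 / 2 sessions = 2 per session. Section 5.4.1: baseline + final = 2, repeated in session 2. Section 6.4.2 states 2. The three places agree.

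**2. Count what the analysis needs.** Write B for baseline, S for post-stress and P for post-treatment. The within-session differences are

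- D1 = P − B
- D2 = P − S

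and the between-session contrasts are D1(tACS) − D1(sham) and D2(tACS) − D2(sham). Together they use B, S and P, so three distinct samples per session. The genotyping sample supplies none of these, since it is a DNA sample taken once.

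**3. Check which differences two samples allow, by task position.**

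| Task position | First sample is | Final sample is | P − B | P − S |
|---|---|---|---|---|
| After first sample, before stimulation | B | P | yes | no |
| After stimulation, before final sample | B | P and S at once | yes | not a separate quantity |
| Before first sample | S | P | no | yes |
| After final sample, or not given | B | P | yes | no |

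Two samples give 2 − 1 = 1 within-session difference, and three give 3 − 1 = 2. In every row at most one of the two planned contrasts is available. With the first sample labelled baseline, as in 5.4.1, the one lost is P − S.

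**4. Size.** For k biomarkers, 2k contrasts are planned and k are computable, so half are lost whatever the size of the cytokine panel (which is not given). Counting the three named classes once each: 6 planned, 3 computable. For 20 participants completing both sessions:

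- scheduled: 2 × 2 × 20 = 80 samples
- needed: 3 × 2 × 20 = 120 samples
- shortfall: 120 − 80 = 40

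**5. How far the silence on the task can be read.** The procedural lists are not exhaustive. Section 7.3 has "After participants have completed the questionnaires, they will be comfortably seated", and Appendix A lists baseline questionnaires on day 1, yet the session 1 steps mention no questionnaire before stimulation. Conversely, the session 1 steps include "Participants will then undergo a ten-minute resting state block to record EEG activity", and Appendix A has no row for it. Absence from these lists therefore shows that the position is not stated there. It does not show that the task is not given.

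**6. A lesser mismatch in the same paragraph.** Section 11.1.2 words its conclusion as an effect on NK cell count. That is not an outcome in section 11.1.1 and is not among the saliva assays in section 6.4.2.

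**The case against.** The strongest reply is that the trial can still answer its stated question. The null in section 2.4 is general: it concerns immune response under tACS against sham and does not mention a post-stress sample. The rejection rule in section 11.1.2 requires a difference between conditions in within-session activity of any biomarker, not both differences. Two samples deliver a change per session, and this is a pilot aimed at estimation. All of this stands. A reader might infer that the primary analysis fails altogether or that the null cannot be tested; the documents do not support that, because final minus baseline remains usable as a paired comparison.

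The second reply concerns the stress task. Figure 1 and the attached documents are not available here, and a session timeline could be in them, although section 4 cites the figure for the arms. Section 11.1.2 also carries a hint: comparing the post-treatment sample with a post-stress sample to isolate the effect of stimulation suggests the order baseline, stress, stimulation. This stands as a limit on the second half of the point. It is still an inference, since no section states the order. Nor does it remove the conflict over samples: under that very order, two samples leave out the post-stress one. A figure showing a third sample would itself contradict sections 5.4.1, 5.4.2 and 6.4.2 and Appendix A.

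**Conclusion.** The plan contradicts itself. Section 11.1.2 needs three biomarker samples per session and the procedures consistently provide two, so at most one of two planned contrasts per biomarker can be computed. For 20 completers the schedule is 40 samples short of what the analysis requires. Confidence in this count is high; it rests only on the plain reading of the sections cited and holds for any position of the task.

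That the task's position is unstated is held with moderate confidence and only for the text available. A reader might go further and conclude that the task has been dropped. The documents do not support that: section 8.2.1 says that it will be given, section 6.1 refers to its effect, and the procedural lists omit other steps too. What follows is narrower. The meaning of final minus first sample is unsettled, and whether the stress question in the title is addressed depends on a position that has to be stated.

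This must be settled before data collection, because part of a stated primary analysis cannot be run if the plan is followed as written, and the least costly correction is one of text.

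**What to change.** Before data collection, reconcile sections 5.4.1, 5.4.2, 6.1, 6.4.2, 7.3, 8.2.1 and 11.1.2 and Appendix A on whether and when the task is given and how many biomarker samples are taken. This review does not say which schedule is right.

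**If two samples are kept,** delete the contrast that cannot be computed and name the tACS-minus-sham difference in final minus first sample as the one primary contrast for each biomarker. Describe it by the task's stated position:

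- (a) after the first sample and before stimulation: net change over stress and recovery under stimulation;
- (b) after stimulation and before the final sample: net change including reactivity to stress after stimulation;
- (c) before the first sample: recovery after stress, with that sample relabelled post-stress;
- (d) not given, or after the final sample: no response to the task, so narrow the title and objective; if the task is not given, also remove it from section 8.2.1 and from the STAI rationale in section 6.1.

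**If both contrasts are kept,** state the task and a third sample, with their times, in sections 5.4.1, 5.4.2 and 6.4.2 and in Appendix A.

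In every case, replace NK cell count in section 11.1.2 with the assayed biomarkers.

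**Cost.** The two-sample route needs text changes and an IRB amendment, since section 9.1 ties conduct to the approved application; it adds no samples. Option (d) also gives up the stress question in the title. The three-sample route needs the same amendment plus 40 more saliva samples and their assays if all 20 participants complete both sessions.
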